10.3. Causality

The relationship of each adverse event to the trial medication must be determined by a medically qualified individual according to the following definitions:

Relationship to Drug	Comment
Definitely	Previously known toxicity of agent; or an event that follows a reasonable temporal sequence from administration of the drug; that follows a known or expected response pattern to the suspected drug; that is confirmed by stopping or reducing the dosage of the drug; and that is not explained by any other reasonable hypothesis.
Probably	An event that follows a reasonable temporal sequence from administration of the drug; that follows a known or expected response pattern to the suspected drug; that is confirmed by stopping or reducing the dosage of the drug; and that is unlikely to be explained by the known characteristics of the subject's clinical state or by other interventions.
Possibly	An event that follows a reasonable temporal sequence from administration of the drug; that follows a known or expected response pattern to that suspected drug; but that could readily have been produced by a number of other factors.
Unrelated	An event that can be determined with certainty to have no relationship to the study drug.

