7.6. Fluciclovine (^{18}F) PET/CT

The PET/CT will be acquired on the highest quality scanner available in the participating institution. The participant will be required to fast for at least 4 hours prior to the scan, drinking only sips of water within 4 hours of the scan if needed for administration of medications, and not exercise from the day before the scan through to the time of the scan. The participant will be cannulated, preferably in the right arm, and receive one dose of fluciclovine (^{18}F) diluted up to 10 mL injected by intravenous push (5-10 seconds) via the cannula with arms down followed by $\geq 10\text{mL}$ flush [54]. The participant will be scanned in the supine position in the direction of mid-thigh to skull base, with the arms positioned overhead following the dose and flush. The uptake time should be 3 to 5 minutes with a goal of 4 minutes from the end of the dose. For the PET acquisition, participants will be imaged for approximately 25 minutes. For the CT parameters, a high-quality unenhanced CT will be employed. Further details on the PET/CT acquisition will be given in the Study Imaging Manual.

Vital signs, examination of the injection site and review of AE/SAEs will be performed immediately post scan and at 60(± 5) minutes, 90(± 5) minutes and 120(± 5) minutes post-injection. All images obtained during the trial will be retained for use in this research and may be used for future approved research studies.

Analysis

Image interpretation will be based on guidelines derived from an international fluciclovine (^{18}F) reader consensus meeting held in June 2014 [54]. All readers will undergo training in interpretation of fluciclovine (^{18}F) scans, and will have a training set available for reference.

Primary evaluation and reporting of the PET/CT scan will be site-based (as per standard of care). The clinical team should make the revised treatment decision on the site-based report.

The fluciclovine (^{18}F) PET/CT scan will be centrally reported at the end of the study, blinded to the original report. Copies of the fluciclovine (^{18}F) PET/CT will be transferred from the host site for this purpose. Copies of the original report will also be transferred, as this data will be used to determine inter-reader agreement.

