10. SAFETY REPORTING

10.1. Definitions

Adverse Event (AE)	Any untoward medical occurrence in a participant to whom a medicinal product has been administered, including occurrences which are not necessarily caused by or related to that product.
Adverse Reaction (AR)	
An untoward and unintended response in a participant to an investigational medicinal product which is related to any dose administered to that participant.
 
The phrase "response to an investigational medicinal product" means that a causal relationship between a trial medication and an AE is at least a reasonable possibility, i.e. the relationship cannot be ruled out.
 
All cases judged by either the reporting medically qualified professional or the Sponsor as having a reasonable suspected causal relationship to the trial medication qualify as adverse reactions.

Serious Adverse Event (SAE)	
A serious adverse event is any untoward medical occurrence that:
 
 • results in death • is life-threatening • requires inpatient hospitalisation or prolongation of existing hospitalisation • results in persistent or significant disability/incapacity • consists of a congenital anomaly or birth defect. 
Other 'important medical events' may also be considered serious if they jeopardise the participant or require an intervention to prevent one of the above consequences.
 
NOTE: The term "life-threatening" in the definition of "serious" refers to an event in which the participant was at risk of death at the time of the event; it does not refer to an event which hypothetically might have caused death if it were more severe.

Serious Adverse Reaction (SAR)	An adverse event that is both serious and, in the opinion of the reporting Investigator, believed with reasonable probability to be due to one of the trial treatments, based on the information provided.
Suspected Unexpected	A serious adverse reaction, the nature and severity of which is not

Serious Adverse Reaction (SUSAR)	consistent with the information about the medicinal product in question set out: 
 • in the case of a product with a marketing authorisation, in the summary of product characteristics (SmPC) for that product • in the case of any other investigational medicinal product, in the investigator’s brochure (IB) relating to the trial in question.
----------------------------------	---

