6.1 Adverse Events

Adverse events (AE) will be coded using the Medical Dictionary for Regulatory Activities (MedDRA) version 17.1.

A treatment-emergent adverse event (TEAE) is defined as an AE with start date/time on or after the start/time of fluciclovine (¹⁸F) administration, or AEs with worsening intensity on or after the start date/time of fluciclovine (¹⁸F) administration.

AEs with unknown start date/time will be assumed to be treatment-emergent unless the end date/time is known to be before the fluciclovine (¹⁸F) administration.

Summary tables will be produced for all TEAEs occurring up to 42 days (i.e. occurring between day 1 and day 43) after the fluciclovine (¹⁸F) administration.

An overall summary of TEAEs will be created including:

- number of TEAEs and number of subjects with TEAEs,
- number of TEAEs and number of subjects with TEAEs associated with the injection site,
- number of serious TEAEs and number of subjects with serious TEAEs,
- number of subjects with TEAEs by CTCAE grade (Grade 1 to Grade 5),
- number of subjects with TEAEs by relationship to fluciclovine (unrelated, possibly related, probably related, definitely related and related, where related adverse events are those classified as possibly, probably and definitely related to fluciclovine ¹⁸F)

The number and percentage of subjects experiencing TEAEs will be presented by system organ class (SOC) and preferred term (PT). System organ class and preferred term will be presented in decreasing frequency of the total number of subjects with TEAEs. If a subject experienced more than one treatment-emergent adverse event, the subject will be counted once for each system organ class and once for each preferred term.

The number and percentage of subjects experiencing TEAEs will be presented by SOC, PT and CTCAE grade. SOC and PT will be presented in decreasing frequency of the total number of subjects with TEAEs. If a subject experienced more than one TEAE, the subject will be counted once for each SOC and once for each PT at the worst severity.

The number and percentage of subjects experiencing TEAEs will be presented by SOC, PT and relationship to study drug. SOC and PT will be presented in decreasing frequency of the total number of subjects with TEAEs. If a subject experienced more than one TEAE, the subject will be counted once for each SOC and once for each PT at the closest relationship to study drug.

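### The causality scale in Protocol 10.3 does not fit a single bolus and leaves a plausible reaction of a new kind without any class, in conflict with 10.1

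*Protocol*

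**What the plan says.** Protocol 10.3 is not offered as guidance. The relationship of each adverse event to the trial medication "must be determined by a medically qualified individual according to the following definitions". There are four classes.

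- **'Definitely'** has two routes: "Previously known toxicity of agent; or an event that follows a reasonable temporal sequence from administration of the drug". The second route goes on to require an event "that follows a known or expected response pattern to the suspected drug; that is confirmed by stopping or reducing the dosage of the drug", with no other reasonable explanation.
- **'Probably'** requires a reasonable time sequence, the same known or expected pattern, the same confirmation by stopping or reducing the dosage, and an alternative explanation that is unlikely.
- **'Possibly'** requires a reasonable time sequence and an event "that follows a known or expected response pattern to that suspected drug; but that could readily have been produced by a number of other factors".
- The fourth class, **'Unrelated'**, is "An event that can be determined with certainty to have no relationship to the study drug".

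Protocol 7.6 describes the exposure: "The participant will be cannulated, preferably in the right arm, and receive one dose of fluciclovine". Sections 7.6 and 9.1 give it as an intravenous push over 5–10 seconds.

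Protocol 10.1 uses a different test. An event is an adverse reaction when a causal relationship "is at least a reasonable possibility, i.e. the relationship cannot be ruled out". It adds that cases judged by the reporting professional or by the sponsor to have a reasonable suspected causal relationship also qualify.

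SAP 6.1 tabulates treatment-emergent events at each of the four levels and as a pooled group, "where related adverse events are those classified as possibly, probably and definitely related to fluciclovine".

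**The concern.** The definitions read as if written for a drug given repeatedly, where the dose can be withdrawn and the effect watched. Here the whole dose is in the patient within seconds. A class that depends on dechallenge cannot be used, yet the SAP reserves a line for it.

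The second difficulty matters more. Safety of the injection is a secondary objective, and one use of a safety database is to show reactions that were not anticipated. The scale asks for a known or expected pattern in every related class, apart from the known-toxicity route, which asks for even more prior knowledge. A new kind of reaction is therefore the event the scale handles worst. Two things depend on the class entered: the SAP tables by relationship, and, in part, the rule in Protocol 10.4 that related events are followed until they resolve or become stable.

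**Working it through.** There is no figure in the plan to reproduce and no arithmetic beyond counting. The check applies each definition in turn to two situations.

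**Inputs.** The four definitions are from Protocol 10.3, the single push from 7.6 and 9.1, the adverse-reaction test from 10.1, and the pooling rule from SAP 6.1. Within each definition the conditions are separated by semicolons and closed by 'and' or 'but', so all are required. In 'Definitely', the 'or' after known toxicity is read as making that route sufficient alone, which is the reading more favourable to the protocol.

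| Route (10.3) | Known toxicity or pattern needed? | Dechallenge needed? | (a) Reachable after one completed push? | (b) Open to a plausible reaction of a new kind? |
|---|---|---|---|---|
| 'Definitely', first route | Yes, known toxicity | No | Yes | No |
| 'Definitely', second route | Yes, pattern | Yes | No | No |
| 'Probably' | Yes, pattern | Yes | No | No |
| 'Possibly' | Yes, pattern | No | Yes | No |
| 'Unrelated' | No | No | Yes | No, certainty is lacking |

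**(a) Single bolus.** Two of the four related routes are closed for every participant, whatever the number dosed. 'Definitely' survives through known toxicity and 'Possibly' survives in full. 'Probably' has no other route, so on the literal text the SAP's 'probably related' line is zero by construction.

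**(b) New kind of reaction.** All four related routes fail, and 'Unrelated' fails as well: 0 of 4 classes fit. Under 10.1 the same event is an adverse reaction, because the relationship has not been excluded. The two sections give incompatible answers for one event.

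**What the SAP then does.** SAP 6.1 gives a default for an unknown start date (treat the event as treatment-emergent) but none for absent causality. SAP section 2 makes no general imputation, and the opening of the SAP's safety section counts subjects only where data are available. Related is built by adding three classes, so an event with no code is not in the sum.

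**Effect of the proposed SAP rule.** Counting everything not 'Unrelated' equals the present three-class sum plus events without a valid causality code. On recorded data, the pooled count can rise only by the number of such events. The documents give no event counts, so that number cannot be stated.

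**The case against.** The strongest reply is that little turns on this.

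- **Expedited reporting.** A reader might infer that a SUSAR can never be classed as related and so may go unreported. The documents do not support that. Section 10.1 lets the reporting professional or the sponsor judge causality without reference to the 10.3 scale. Section 10.5 sends all SAEs to the sponsor within 24 hours whatever their class, 10.6 makes the sponsor responsible for SUSAR reports, and 10.7 adds a quarterly and cumulative sponsor review of all SAEs. This part of the reply stands in full.
- **Unexpected is not the same as patternless.** Section 10.1 ties unexpectedness to nature and severity against the product information, while 10.3 ties the pattern to no document. A listed reaction such as headache or an injection-site reaction (9.1), occurring with unexpected severity, may still follow a known pattern and be classed as related. An assessor could also read a general hypersensitivity picture as a known pattern. This stands too. The gap is confined to reactions of a new kind on a literal reading, although relying on a loose reading invites differences between sites.
- **The empty line.** SAP 6.1 pools the three related classes, so an event with a known pattern that cannot be 'Probably' can still be counted through another class. That also stands. The empty line alone changes little in a descriptive analysis.
- **Missing codes would be noticed.** Central monitoring (13.2) checks forms for missing data, and all adverse events are listed (SAP 6.1). This helps only partly: a query asks the site for a class, and no class is valid for the event in question.

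**Conclusion.** The point holds as a conflict of wording with a limited effect on the safety tables. On the literal text, 1 of 4 classes ('Probably') is unreachable and 1 of 2 routes to 'Definitely' is closed. A plausible reaction of a new kind fits 0 of 4 classes, although 10.1 calls it an adverse reaction. Such an event has no valid code and can be left out of the SAP's related count.

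This rests on three assumptions: that 10.3 is applied as written, that its conditions are cumulative, and that known toxicity is a sufficient route by itself. If that last reading is wrong, 'Definitely' is also closed after one push and only 'Possibly' remains.

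The documents do not show that any event was miscoded, how many might be affected, or that regulatory reporting failed. The correction is worth making because it is inexpensive and any remaining error then leans towards counting an event as related.

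**What to change.** **Protocol 10.3.** Delete the clause on stopping or reducing the dosage from 'Definitely' and 'Probably'. Remove the known-or-expected-pattern requirement from 'Possibly'. Add that any event whose relationship cannot be ruled out is at least 'Possibly', so that 10.3 agrees with 10.1.

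**SAP 6.1.** Define related as every treatment-emergent event not classed 'Unrelated', including events with missing causality, and show the number with missing causality on its own line.

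**Timing.** SAP Addendum 2, dated 08MAR2019, describes analyses added after database lock. Investigator assessments should therefore not be recoded. Present the revised definition as a documented post-lock supplementary tabulation beside the planned one, using the existing adverse-event listing. State in the report that the 'probably related' category could not be reached under the literal 10.3 text.

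**Cost.** Wording in two places and one additional table; no new data, visits or patients. The related count may rise slightly. One limit remains: an event that a site entered as 'Unrelated' for want of a better class is not recovered by this tabulation and can be seen only in the listing.

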10.4. Procedures for Recording Adverse Events

All AEs observed by the investigator or reported by the patient up to 1 month after fluciclovine (¹⁸F) PET/CT are reported on the case report forms. A member of the research team will contact the participant by telephone 24 -72 hours and 1 month after completion of fluciclovine (¹⁸F) PET/CT to record any AEs that may have occurred after leaving the hospital. Patients will also attend a clinic visit 14 days post scan. All AEs reported by the patient will be clearly documented on the patient CRFs. The following information will be recorded: description, date of onset and end date, severity, investigator assessment of relatedness to fluciclovine (¹⁸F) injection, other suspect drug or device and action taken. Follow-up information should be provided as necessary.

AE severity

The National Cancer Institute's Common Terminology Criteria for Adverse Events (CTCAE) Version 4.03 (June 14, 2010) will be used to assess and grade event severity, including laboratory abnormalities judged to be clinically significant. The severity grading is provided below (Table 1).

Table 1. CTCAE (V4.03) AE Severity Grading

Severity (Toxicity Grade)	Description
Grade 1	Mild; asymptomatic or mild symptoms; clinical or diagnostic observations only; intervention not indicated.
Grade 2	Moderate; minimal, local or non-invasive intervention indicated; limiting age-appropriate instrumental ADL.*
Grade 3	Severe or medically significant but not immediately life-threatening; hospitalisation or prolongation of hospitalization indicated; disabling; limiting self care ADL**.
Grade 4	Life-threatening consequences; urgent intervention indicated.
Grade 5	Death related to AE

*Instrumental ADL refer to preparing meals, shopping for groceries or clothes, using the telephone, managing money, etc.

** Self care ADL refer to bathing, dressing and undressing, feeding self, using the toilet, taking medications, and not bedridden.

If the experience is not covered in the modified criteria, the guidelines shown in Table 2 below will be used to grade severity. It should be pointed out that the term “severe” is a measure of intensity and that a severe event is not necessarily serious.

Table 2. AE Severity Grading

Severity (Toxicity Grade)	Description
Mild (1)	Transient or mild discomfort; no limitation in activity; no medical intervention or therapy required. The subject may be aware of the sign or symptom but tolerates it reasonably well.
Moderate (2)	Mild to moderate limitation in activity, no or minimal medical intervention/therapy required.
Severe (3)	Marked limitation in activity, medical intervention/therapy required, hospitalizations possible.
Life-threatening (4)	The subject is at risk of death due to the adverse experience as it occurred. This does not refer to an experience that hypothetically might have caused death if it were more severe.
Death (5)	Death related to AE

AEs considered related to fluciclovine (¹⁸F) injection as judged by a medically qualified investigator or the Sponsor will be followed either until resolution, or the event is considered stable.

It will be left to the investigator's clinical judgment whether or not an AE/ AR is of sufficient severity to require the patient's removal from PET/CT scanning. A participant may also voluntarily withdraw from study procedures if they tolerate it poorly. Further details of withdrawal are presented in Section 7.7.

In the event of symptoms arising, participants will be given appropriate care and medical supervision until symptoms resolve, or the condition becomes stable. Every effort will be made to gather outcome data on patients through study follow-up, or general practitioner/ hospital staff unless the participant has specifically withdrawn consent to such efforts.

10.5. Reporting Procedures for Serious Adverse Events

All SAEs following fluciclovine (¹⁸F) PET/CT must be reported on the SAE reporting form within 24 hours of the Site Study Team becoming aware of the event. All SAE information must be recorded on an SAE form and faxed, or scanned and emailed to:

Blue Earth Diagnostics SAE E mail: [contact]

[contact]

[contact]

Additional and further requested information (follow-up or corrections to the original case) will be detailed on a new SAE Report Form and faxed/emailed to the same address.

10.6. SUSAR Reporting

Blue Earth Diagnostics will be responsible for reporting of all SUSARs to the relevant Competent Authority (MHRA in the UK) and to the REC and other parties as applicable. For fatal and life-threatening SUSARS, this will be done no later than 7 calendar days after the Sponsor or delegate is first aware of the reaction. Any additional relevant information will be reported within 8 calendar days of the initial report. All other SUSARs will be reported within 15 calendar days.

Principal Investigators will be informed of all SUSARs for the relevant IMP for all studies with the same Sponsor, whether or not the event occurred in the current study.

10.7. Safety Monitoring Committee

The Sponsor will conduct a review of all SAEs for the trial reported during the quarter and cumulatively. The aims of this committee include:

- To pick up any trends, such as increases in un/expected events, and take appropriate action

- To seek additional advice or information from investigators where required
- To evaluate the risk of the trial continuing and take appropriate action where necessary

10.8. Development Safety Update Reports (DSURs)

In addition to the expedited reporting above Blue Earth Diagnostics will submit DSURs once a year throughout the clinical trial, or on request, to the Competent Authority (MHRA in the UK), to the Chief Investigator and to the Co-Investigator at each site. The CI is responsible for submitting these to the Ethics Committee and the Host NHS Trust.

11. STATISTICS AND ANALYSIS

Prior to the conduct of the planned interim analysis, a detailed Statistical Analysis Plan (SAP) will be written describing all analyses that will be performed for both the interim analysis and the final analysis of all study data.

11.1. Sample size

For the primary objective of treatment change evaluation, a minimum of 171 patients with complete primary endpoint data will be required to allow for a width of +/-6% in a two-sided 95% C.I. This is based on the conservative assumption that 20% of patients will have a treatment change, as fluciclovine (¹⁸F) PET/CT has been shown to upstage 25.7% of patients with recurrent prostate cancer [49], and also based on the management change studies reported on choline PET/CT (section 3). The aim is to recruit 180 patients for this trial, based on an anticipated primary endpoint drop-out rate of 5%.

